## Causality Assessment

The relationship between the use of the investigational device and the occurrence of each AE/SAE shall be assessed by the investigator and the sponsor and classified as investigational device related or not related to investigational device.

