## 4.4 Investigational Device

### 4.4.1 Summary description of the Investigational Device(s) and Comparator(s)

#### Investigational Device - Exufiber®

Gelling Fibre Dressing

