### Comparator - Aquacel® Extra™

Aquacel® Extra™ Hydrofiber® Dressing with Strengthening Fibre is a soft, sterile, non-woven pad dressing composed of sodium carboxymethylcellulose and regenerated cellulose fibre for strengthening. This conformable and highly absorbent dressing absorbs wound fluid and transforms into a soft gel, which maintains a moist environment to support the body's healing process and aid in the removal of nonviable tissue from the wound (autolytic debridement), without damaging newly formed tissue.

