#### **4.4.3 Accountability**

Accountability will be performed on the Investigational Device (Exufiber®) and the comparator (Aquacel® Extra) provided to the investigation site by Mölnlycke Health Care free of charge.

The sites will be provided with the size 10x10 cm free of charge for both Exufiber® and Aquacel® Extra. More than one dressing can be used on a wound when deemed necessary.

The Principal Investigator is responsible for establishing routines for correct handling of the Investigational Devices to ensure that:

- Deliveries of products from Mölnlycke Health Care are correctly received
- Accurate records are maintained, accounting for the receipt of the investigational device (a delivery note will be provided with the shipments) and for the return or destruction of the products.
- Investigational Devices are handled and stored safely, properly and in agreement with the provided storage conditions.
- The Investigational Devices are prescribed only by the Principal Investigator or by a person authorized to do so by the Principal Investigator.

- 
- The Principal Investigator will under no circumstances allow the Investigational Devices to be used for other purposes than directed by this Clinical Investigation Plan.
  - Use of Investigational Devices must be documented on a subject specific level in the eCRF. Information to be documented includes identification of the subject using the device, identification and quantity of the medical device dispensed, date of dispensing and documentation of returned devices (if any) from the subject

Returned and unused products are accounted for and returned to Mölnlycke Health Care for destruction. All returned or destroyed products should be documented on a specific form provided by Mölnlycke Health Care.

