### Adverse Event (AE)

Any untoward medical occurrence, unintended disease or injury, or untoward clinical signs (including abnormal laboratory findings) in subjects, users or other persons, whether or not related to the investigational medical device

Note:

- This definition includes events related to the investigational medical device or the comparator.
- This definition includes events related to the procedures involved.
- For users or other persons, this definition is restricted to events related to investigational medical devices.

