### Adverse Device Effect (ADE)

Adverse Event related to the use of an investigational medical device

Note:

- This definition includes adverse events resulting from insufficient or inadequate instructions for use, deployment, implantation, or operation, or any malfunction of the investigational medical device.
- This definition includes any event resulting from use error or from intentional misuse of the investigational medical device.

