**Serious Adverse Device Effect (SADE)**

Adverse Device Effect that has resulted in any of the consequences characteristic of a Serious Adverse Event.

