## 6.4 Safety

All safety variables will be summarized and analysed descriptively by treatment group on the safety population.

The number of subjects reporting one or more AE/ADE/SAE/SADE/DD will be summarised by treatment group using frequency counts. If very few AE/ADE/SAE/SADE/DD these will only be listed.

The incidence (%) of AE/ADE/SAE/SADE/DD reported during the investigation will be summarised in an overview table and by treatment group.

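### ADE, SADE and causality are defined against the investigational device alone, so the by-arm ADE and SADE rows may not treat Exufiber and Aquacel Extra alike

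*Protocol*

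**What the plan says.** Protocol section 8 sets the safety definitions, and four entries matter here.

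- Adverse event: the note to the definition says "This definition includes events related to the investigational medical device or the comparator". Both products are covered, and they are named as two separate things.
- ADE: "Adverse Event related to the use of an investigational medical device". The comparator is not mentioned.
- SADE: "Adverse Device Effect that has resulted in any of the consequences characteristic of a Serious Adverse Event". It is a subset of the ADE and has the same scope.
- Causality: the investigator and the sponsor assess each event, which is then "classified as investigational device related or not related to investigational device". There are two categories and none for the comparator.

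Section 4.4.1 fixes the terms under the subheadings "Investigational Device - Exufiber" and "Comparator - Aquacel® Extra™". The opening of section 4.4.3 (Accountability) makes the same split.

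SAP section 5.3.3 lists the safety variables and refers to protocol section 8 for their definitions; it has none of its own. SAP section 6.4 then states: "The number of subjects reporting one or more AE/ADE/SAE/SADE/DD will be summarised by treatment group using frequency counts". It describes the safety analysis as descriptive and allows very sparse events to be listed only.

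**The concern.** The adverse event note shows that the authors named the comparator where they meant to include it. The ADE, SADE and causality entries leave it out. A site that follows the text as written has only one place for a reaction caused by Aquacel Extra: unrelated. The event is still recorded as an adverse event, but it does not become an ADE, and if serious it does not become a SADE.

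The SAP tabulates both classes by arm, so one arm can accrue device effects while the other, for ordinary reactions, cannot. A reader of that table would take a difference in definition for a difference in tolerability, to the disadvantage of the sponsor's own product. Safety is part of the comparison in the primary objective (protocol section 2), and ADEs, including serious ones, are a listed secondary endpoint. The introduction says the trial supports a reimbursement renewal in France, so the table will have outside readers. If the eCRF records relatedness to Exufiber only, the missing comparator classification cannot be recovered from the adverse event counts.

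**Working it through.** The plan states no figure on this point, so there is none to reproduce. The check is a reading of the definitions, followed by an illustration of scale.

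**Step 1: follow one event through the text.** Take the same dressing-related skin reaction in each arm.

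| Question | Exufiber arm | Aquacel Extra arm, literal reading |
|---|---|---|
| Adverse event? | Yes | Yes (the note covers the comparator) |
| Causality category | Related | Not related |
| ADE? | Yes | No |
| SADE, if serious? | Yes | No |
| Counted as an SAE, if serious? | Yes | Yes (reported whatever the causality) |

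The arms part only at the causality row and at the two classes that depend on it.

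**Step 2: scale.** Inputs:

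- 106 subjects per group, from protocol section 4.8.2 and SAP section 6.5. The safety population may differ somewhat.
- A true dressing-related event rate r, equal in the two arms. The documents give no such rate; 2%, 5% and 10% are assumptions.

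The expected count in an arm judged against its own dressing is 106 × r. For Aquacel Extra under the literal rule, the expected count of ordinary reactions classed as ADEs is 0.

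| Assumed r | 106 × r | Exufiber | Aquacel Extra, literal rule | Aquacel Extra, same rule as Exufiber |
|---|---|---|---|---|
| 2% | 2.12 | about 2 | 0 | about 2 |
| 5% | 5.30 | about 5 | 0 | about 5 |
| 10% | 10.60 | about 11 | 0 | about 11 |

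**Step 3: mixed reading.** Let f be the unknown share of Aquacel Extra reactions that sites class as related because they read the term broadly. The expected difference is 106 × r × (1 − f). It runs from the literal figures above (f = 0) to no difference (f = 1). In this simple model the definitional part shrinks but does not reverse. A reversal would need something more, such as sites in this open trial judging relatedness by different standards for the two products. The documents neither show nor exclude that, so under mixed reading neither size nor direction can be fixed from the text.

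**The case against.** The strongest reply is that the protocol does not use the term strictly. Section 4.4 carries the investigational device in its title but describes both products. After its opening sentence, section 4.4.3 switches to a plural in its rules on handling, prescribing and subject-level records, and that plural most naturally covers both dressings. The device deficiency procedure in section 8 sorts deficiencies by whether the investigational device was used by a subject, which works poorly if Aquacel Extra is excluded. A two-arm tabulation of ADEs also suggests that the authors meant the study dressing. This has force: the intent may well have been symmetric. It does not settle the matter, because section 8 nowhere extends the term and its own adverse event note separates the two products.

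Three stronger readings are tempting, and the documents do not support them.

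- *The comparator's ADE and SADE counts must be zero.* The loose usage leaves room for sites to class Aquacel Extra reactions as related. Device deficiency is defined for any medical device, and section 8 has deficiencies that might have led to a SADE reported as a SADE, so the comparator has one written route into SADE reporting. That route covers potential-SADE deficiencies, not ordinary reactions.
- *The safety comparison is invalid.* Adverse events cover both products, serious adverse events are reported whatever their cause, and device deficiencies apply to either product. Peri-wound skin, pain at dressing removal and signs of local infection follow the same schedule in both arms.
- *The artefact would be statistically significant.* Two-sided Fisher exact p-values for 2, 5 and 11 vs 0 out of 106 are 0.50, 0.060 and 0.0007. They depend on the assumed rate, and the SAP plans no safety test.

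The eCRF causality item and Appendix C are not in the supplied text. If the item already asks about either dressing, the data are sound and only the wording needs correcting.

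**Conclusion.** The concern holds for the descriptive ADE and SADE rows and goes no further. Followed literally, section 8 classifies ordinary dressing reactions by different rules in the two arms, and the SAP carries that into a by-arm table that would tend to show an excess for Exufiber. The illustrated excess, about 2, 5 or 11 subjects in 106, rests on three assumptions: equal true rates, the literal reading at every site, and the chosen rates themselves. How the sites actually classified comparator reactions cannot be told from these documents.

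**What to change.** - **Protocol section 8:** define ADE, SADE and causality against the study dressing the subject received, Exufiber or Aquacel Extra, assessed the same way in both arms.
- **SAP section 6.4:** state that this relatedness variable feeds the by-arm ADE and SADE tables. If a regulatory count for Exufiber alone is needed, report it separately and label it as such.
- **eCRF:** confirm that the causality item matches the revised definition. If it has recorded relatedness to Exufiber only, relatedness for events in the Aquacel Extra arm would need to be assessed before database lock.

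The cost is a wording change in two sections and one check of the eCRF. Visits, sample size and the efficacy analysis are untouched.

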## 1. LIST OF ABBREVIATIONS

Abbreviation or special term	Explanation
ADE	Adverse Device Effect
AE	Adverse Event
CIP	Clinical Investigation Plan
DD	Device Deficiency
e-CRF	Electronic Case Report Form
EC	Ethics Committee
GWV	Gesellschaft für Versorgungskonzepte in der Wundbehandlung mbH
ICC	Intra-class Correlation Coefficient
ITT	Intention to Treat
PP	Per Protocol
SAE	Serious Adverse Event
SADE	Serious Adverse Device Effect
VAS	Visual Analogue Scale

## 2. STUDY OBJECTIVES

The overall objective of this non-inferiority investigation is to compare Exufiber® versus Aquacel Extra in terms of efficacy and safety, measured in moderately or strongly exuding venous and mixed ulcers of predominantly venous origin during a period of 6 weeks investigation period.

The primary endpoint is to evaluate wound area reduction (%) from baseline until end of investigation (up to 6 weeks). Wound area reduction will be centrally measured by one blinded independent review using the validated system PictZar®. A second supportive blind review will be done by an independent French expert.

Secondary endpoints are to evaluate;

- Wound area reduction (absolute change in cm^2) from baseline until end of investigation (up to 6 weeks)
- Linear advance of the wound margin according to Gilman's formula (Cardinal et al, 2008) based on the digital photos and calculated by PictZar
- Relative reduction (%) of sloughy tissue
- Percentage of patients with a debrided wound at end of investigation (at least 70% of the wound surface area covered with granulation tissue (confirmed using PictZar). Number of additional debridements used during the investigation. Pain during the debridement and ease of debridement
- Changes from baseline in the condition of the peri-wound skin measured by the following variables; maceration, redness/irritation, blistering, skin stripping, trauma to wound edges
- The level of pain in connection to removal of dressing
- Changes in wound status including exudates management
- Clinician's and subject's opinion related to the dressing
- Cost effectiveness and health economics will be measured using EQ-5D-3L and wound management related material use
- Tolerance such as adverse events and adverse device effects including those reported to be serious

Ancillary objective

- In order to support that wound area reduction at week 6 is a clinically relevant parameter to predict long-term favorable wound healing, a sub-group of at least 50 subjects from the wound care centers owned by GWV (Gesellschaft für Versorgungskonzepte in der Wundbehandlung mbH) in Germany will be assessed at 24 weeks post-inclusion. Favorable trajectory will be defined by an area regression, compared to baseline, of 80% or more at week 24. Additionally, wound closure (100% re-epithelialization confirmed by photo) rate will also be evaluated. All these parameters will be centrally measured on photos according to previously described procedure.

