## **4.8 Statistical Methods and Determination of Sample Size**

### **4.8.1 Statistical Evaluation**

The intent-to-treat (ITT) population is defined as all randomised patients with at least one follow up planimetry value (from the validated tool PictZar) and the per-protocol (PP) population as all patients with a wound area measurement till the fourth week of follow-up, at least. Subjects with significant protocol deviations will be excluded from the PP population.

PictZar has received 510k notification and is compliant with CFR Part 11.

In this non-inferiority study the primary efficacy analysis will be constructing a two sided 95% confidence interval, using Fisher's non-parametric permutation test, for between-treatment differences (Exufiber® - Aquacel® Extra) in the mean percentage area change from baseline to 6 weeks. This means that if the lower limit of this confidence interval is greater than 12% non-inferiority will be established.

All the main efficacy analyses will be performed on the PP population. Complementary efficacy analyses will be performed on the ITT-population for further confirmation. The ITT and PP analyses will have to provide the same results to establish the non-inferiority. All safety analysis will be performed on the safety population.

Superiority can be concluded if the lower bound of a two sided 95% confidence interval for between-treatment differences (Exufiber® - Aquacel® Extra) in the mean percentage area change from baseline to 6 weeks does not overpass zero.

There will also be a second blinded assessment carried out (not using the PictZar system) that will support the main analysis done by PictZar.

For secondary variables Fishers exact test for dichotomous variables, Mantel-Haenszel chi-square test for ordered categorical variables and Pearson Chi-square test for non-ordered categorical variables and Fisher's non-parametric permutation will be used for continuous variables.

If necessary adjustment for baseline variables will be done with multiple logistic regression for dichotomous variables and with covariance analysis for continuous variables.

All statistical tests will be two-sided and conducted at the 5% significance level.

A sub-group analysis by country will be performed.

For the primary endpoint last observation carried forward will be applied for the final measurement. No other imputation methods will be used.

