For all secondary endpoints differences between Exufiber® and Aquacel® Extra will be analyzed with the statistical methods given above and 95% confidence interval for the differences between the two groups will be given when appropriate.

The distribution of continuous variables as for changes in continuous variables will be given as mean, SD, median, minimum and maximum and as number and percentages for categorical variables.

Other endpoints will be summarized using descriptive statistics only.

A complete statistical analysis plan (SAP) with the details for all analyses for the whole study will be finalized before first patient in.

A blinded observer will do the measurements of the primary endpoint based on digital photos uploaded in the electronic CRF. The blinded observer will not know the treatment that each subject received.

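### Incidence of AEs, ADEs, SAEs and SADEs has no planned between-arm estimate in the SAP, although tolerance is a listed secondary endpoint and protocol 4.8.1 says differences will be analysed for all of these

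*SAP*

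**What the plan says.** The objective is comparative on safety: SAP section 2 sets out "to compare Exufiber® versus Aquacel Extra in terms of efficacy and safety", and the protocol synopsis and section 2 give the same aim as the primary objective. All three places list tolerance as a secondary endpoint: "Tolerance such as adverse events and adverse device effects including those reported to be serious".

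Protocol 4.8.1 then states the analysis of secondary endpoints: "For all secondary endpoints differences between Exufiber® and Aquacel® Extra will be analyzed with the statistical methods given above". The same sentence adds that a "95% confidence interval for the differences between the two groups will be given when appropriate". The methods above it include a test for binary outcomes: "For secondary variables Fishers exact test for dichotomous variables". A separate sentence covers what is descriptive only: "Other endpoints will be summarized using descriptive statistics only".

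The SAP treats tolerance differently. It is absent from the secondary efficacy list in 5.3.2, and AEs, ADEs, SAEs, SADEs and device deficiencies appear in 5.3.3 as safety variables. Section 6.4 reads: "All safety variables will be summarized and analysed descriptively by treatment group on the safety population". It goes on to frequency counts and incidence by arm, with listings alone if there are very few events.

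**The concern.** Followed as written, the SAP puts two percentages side by side for an endpoint that its own section 2 calls secondary, and attaches no difference or interval to them. Two misreadings become easy. A chance imbalance may be taken as a signal. Similar percentages may be taken as evidence of equal safety when the data do not exclude a sizeable excess in either arm. The protocol introduction says the trial supports a reimbursement renewal, so an informal reading of equal tolerance could carry weight.

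The rule that few events will only be listed has a similar effect. For the rarer categories, probably SAEs and SADEs, no comparative figure would appear at all.

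**Working it through.** **The texts side by side**

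| Question | Protocol | SAP |
|---|---|---|
| Is tolerance a secondary endpoint? | Yes in synopsis and section 2; missing from the list in 4.6.4; AEs are safety variables in 4.6.5 | Yes in section 2; missing from 5.3.2; AEs are safety variables in 5.3.3 |
| Are arms to be compared on it? | 4.8.1: yes, for all secondary endpoints | 6.1 names between-arm tests for baseline and secondary efficacy variables; 6.3.2 covers only variables in 5.3.2; 6.4 is descriptive |
| Is an interval planned? | 4.8.1: when appropriate | None in 6.4 |
| Over what period? | AEs collected to week 6 in all, to week 24 in at least 50 subjects (4.2.1) | No window stated in 6.4 |

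SAP 6.1 also says, in general words, that intervals for a difference in proportions will be calculated for dichotomous variables. That sentence follows a paragraph about baseline and secondary efficacy variables. Sections 6.2 and 6.3.2 refer back to 6.1, and 6.4 does not. So it cannot be relied on to cover adverse events.

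**The plan's own figure**

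The plan gives no event rate, safety margin or safety power. Its only relevant number is 106 per arm, derived for wound area. With margin 12, SD 35 and 80% power, n = 2(z_α + 0.842)² × 35²/12². With z_α = 1.645 this is 105.2, so 106, which matches. With z_α = 1.96, which corresponds to a two-sided 95% interval, it is 134. That mismatch is a separate matter. Here 106 serves only as an assumed number of dressed subjects per arm.

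**Precision of a difference in incidence**

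With a common incidence p in both arms, the half-width is 1.96 × √(2p(1−p)/106). The incidences are assumptions.

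| Assumed p | 2p(1−p)/106 | Half-width (points) |
|---|---|---|
| 5% | 0.000896 | 5.9 |
| 10% | 0.001698 | 8.1 |
| 20% | 0.003019 | 10.8 |
| 30% | 0.003962 | 12.3 |
| 40% | 0.004528 | 13.2 |

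Newcombe intervals for equal observed counts of 5, 11, 21, 32 and 42 out of 106 agree closely: ±6.4, ±8.5, ±10.8, ±12.2 and ±13.0 points.

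**Two illustrative outcomes (invented counts)**

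- 11 v 11 subjects with an event (10.4% each). The Wilson limits are 5.9% to 17.6%, so the distances from the estimate are 4.48 and 7.26 points. Then √(4.48² + 7.26²) = 8.5, and the interval is −8.5 to +8.5.
- 13 v 7 (12.3% v 6.6%), a difference of 6/106 = +5.7 points. The Wilson limits are 7.31% to 19.86% and 3.24% to 13.01%. Lower limit: 5.66 − √((12.26−7.31)² + (13.01−6.60)²) = −2.4. Upper limit: 5.66 + √((19.86−12.26)² + (6.60−3.24)²) = +14.0.

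**Estimation or testing?**

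Power at 106 per arm, two-sided 5%, normal approximation with pooled variance under the null, for assumed rates: 53% for 10% v 20%, 39% for 20% v 30%, 89% for 20% v 40%. A non-significant test would often say little, so an interval is the more useful summary.

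**The case against.** Descriptive reporting of adverse events is common practice. SAP 6.4 does give the number and percentage of subjects by arm, so a reader could work out a difference and interval. There is no safety hypothesis, and the non-inferiority decision is untouched. All of this stands, and it keeps the point modest.

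The protocol is also not a clear yardstick. A reader might infer that it firmly promises a 95% CI for tolerance and that the SAP alone breaks that promise. The documents do not support this. The analysis of differences in 4.8.1 is unqualified, but the interval is to be given only when appropriate. Protocol 4.6.4 leaves tolerance off its secondary list, 4.6.5 sets adverse events apart, and the SAP follows that structure. The 4.8.1 sentence assigning safety analyses to the safety population fixes the population and does not make the method descriptive.

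What remains is that tolerance is called secondary in three places, 4.8.1 covers all secondary endpoints, and the SAP plans no difference for it.

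**Conclusion.** The point holds as a conflict to reconcile in both documents, limited to the incidence of AEs, ADEs, SAEs and SADEs. It is worth correcting and does not affect the primary analysis.

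A reader might go further and infer that the safety half of the objective gets no comparative estimate at all. That is too strong. Protocol 4.6.6 names four possible outcomes tied to device risk: maceration, prolonged healing, dressing-related pain or trauma, and infection. Maceration, skin stripping, blistering, wound-edge trauma, pain at dressing removal, and stinging or burning are all in SAP 5.3.2 and are compared between arms under 6.3.2. Delayed healing is addressed by the primary endpoint. Of the four, only infection has no named between-arm analysis.

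On size, an added interval would be about ±6 to ±13 percentage points. This assumes 106 dressed subjects per arm and a common incidence between 5% and 40%. Neither an incidence nor a tolerable excess is given in the documents, so these figures show achievable precision only and do not predict a result.

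**What to change.** In SAP 6.4, for the safety population, add the difference (Exufiber minus Aquacel Extra) with a two-sided 95% CI in the proportion of subjects with at least one AE, and likewise for ADE, SAE and SADE. Specify that:

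- the window is the 6-week period common to all subjects, and events from weeks 8 to 24 in the extended subgroup are reported separately;
- the interval is reported also when events are few, alongside any listing, by a method suited to small counts such as Newcombe;
- the intervals are labelled as estimation, with no test and no pass/fail rule.

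Align the protocol as well. Section 4.6.4 should show where tolerance belongs, and 4.8.1 should say that it is analysed by estimation. Otherwise the Fisher's exact test named there for dichotomous secondary variables would still appear to apply. Declaring tolerance descriptive only in the protocol would also remove the contradiction, but would leave the comparative safety aim without stated precision for event incidence.

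The cost is some wording in two documents and a few lines of programming, with no new data. A small downside is a few extra intervals without multiplicity control, which the labelling handles.
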